7. INVESTIGATIONAL PLAN

7.1. Overall Study Design

This double-blind, randomized, placebo-controlled trial will study the safety, tolerability, and efficacy of bardoxolone methyl in qualified patients with WHO Group I CTD-PAH.

Qualified patients will be randomized 1:1 to either bardoxolone methyl or placebo to be administered once daily for 24 weeks. Patients randomized to placebo will remain on placebo throughout the study and undergo sham titration. Patients randomized to bardoxolone methyl will start at 5 mg and will dose-escalate to 10 mg at Week 4, unless contraindicated clinically. Dose de-escalation is permitted during the study if indicated clinically. Please refer to [Section 7.3.1](#) for additional details on dose escalation and dose de-escalation.

All patients in the study will follow the same visit and assessment schedule. Following randomization, patients will be scheduled to be assessed in person during treatment at Weeks 1, 2, 4, 6, 8, 16, and 24 and by telephone contact on Days 3, 10, 21, 31, 38, 84, and 140. Patients will also be scheduled to be assessed at an in-person follow up visit at Week 28, four weeks after the end of treatment.

Patients who complete the study and are treatment-compliant to their assigned dose will be eligible for a separate open-label extension study.

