7.5. Schedule of Assessments

[Table 3](#) lists the overall schedule of assessments for the study.

Table 3: Schedule of Assessments

Assessment	Study Week (Day)	Screen A ^a	Screen B ^b	Day 1 ^c	Week 1 (Phone) Day 3±2	Week 1 Day 7±3	Week 2 (Phone) Day 10±2	Week 2 Day 14±3	Week 3 (Phone) Day 21±2	Week 4 Day 28±3	Week 4 (Phone) Day 31±2	Week 5 (Phone) Day 38±2	Week 6 Day 42±3
Informed consent		X											
Inclusion/ exclusion		X		X ^d									
Demographics and baseline disease characteristics		X											
Prior and Concomitant medications		X	X	X	X	X	X	X	X	X	X	X	X
Current PAH background medications		X	X	X	X	X	X	X	X	X	X	X	X
Medical history		X											
Height		X											
Echocardiogram ^c		X											
Weight at home				X	X	X	X	X	X	X	X	X	X
Dispense weight diary				X		X		X		X			X
Collect/review weight diary					X	X	X	X	X	X	X	X	X
Weight in clinic		X		X		X		X		X			X
ECG		X											
Vital sign measurements		X	X	X		X		X		X			X
Physical exam ^f		X		X		X		X		X			X
Pulmonary function testing		X ^e											
[REDACTED]				X									
Right heart catheterization		X ⁱ											
V/Q scan ^j		X											
Pregnancy test for WOCBP ^k		X	X	X						X			
Study drug administration				X	-----X-----								
Dispense study drug				X						X			
Collect study drug										X			
Telephone contact					X		X		X		X	X	
Adverse event collection				X ^l	X	X	X	X	X	X	X	X	X
Clinical chemistry		X	X	X		X		X		X			X
BNP and NT-Pro BNP		X	X	X		X		X		X			X
Hematology		X	X	X		X		X		X			X
Urinalysis and microscopy		X		X		X		X		X			X
Virus serology		X											
6-min walk test		X	X	X						X			
[REDACTED]		X	X	X						X			
[REDACTED]				X ⁿ		X ^o							
[REDACTED]				X									
WHO functional class ^p		X		X		X		X		X			X
[REDACTED]		X											
[REDACTED]		X		X									
PK samples ^f													

Assessment	Study Week (Day)	Week 8 Day 56±3	Week 12 (Phone) Day 84±2	Week 16 Day 112±3	Week 20 (Phone) Day 140±2	Week 24 (1) or Week 24 Day Prior Visit ^u Day 167±3	Week 24 (2) or End of Treatment Visit ^v Day 168±3	Week 28 Follow-up ^v Day 196±3	
Informed consent									
Inclusion/ exclusion									
Demographics and baseline disease characteristics									
Concomitant medications		X	X	X	X		X	X	
PAH medications		X	X	X	X		X	X	
Medical history									
Height									
Echocardiogram ^c									
Weight at home		X	X	X	X		X		
Dispense weight diary		X		X			X		
Collect/review weight diary		X		X			X		
Weight in clinic		X		X			X	X	
ECG							X	X	
Vital sign measurements		X		X			X	X	

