5.4. Definition of time

For visits (or events) that occur on or after randomization, time is calculated in days as:

$$\text{time} = \text{visit (or event) date} - \text{date of randomization} + 1$$

For visits (or events) that occur prior to randomization, time is calculated in days as:

$$\text{time} = \text{visit (or event) date} - \text{date of randomization}$$

The quantity ‘days since first dose’ is defined as:

- days since first dose = visit (or event) date – date of first + 1

The quantity ‘days since last dose’ is defined as:

days since last dose = visit (or event) date - date of last dose For summaries that present distribution of time expressed in weeks and months, weeks will be defined as days divided by seven and months as days divided by 30.4375.

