12. SAFETY ANALYSES

12.1. Safety variables

Safety variables will include physical examinations, vital sign measurements, ECG, clinical laboratory measurements, concomitant medications, AEs, and SAEs. The safety analyses will include all results collected from randomization through the end of the study. The safety analyses will include only patients in the safety population, with patients classified by whether they received any dose of bardoxolone methyl or not. For laboratory data, vital signs, and ECG data, On-treatment values will be summarized according to the analysis study windows and off-treatment values will be summarized according to the analysis study windows in [Appendix D](#).

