APPENDIX D. CLASSIFICATION OF VISITS

Table D 1. Classification of on treatment visits

Timing of assessment (days relative to first dose of study drug ^a)	Target day	Visit associated with assessment
1	1	Day 1 ^a
2 to 10	7	Week 1
11 to 21	14	Week 2
22 to 35	28	Week 4
36 to 49	42	Week 6
50 to 84	56	Week 8
85 to 139	112	Week 16
140 to 182	168	Week 24 ^a
7 ≤ Days after last dose ≤ 35	28	Week 28 ^c

^a Day 1 is the day of first dose of study drug.

^b Week 24 values is the average of the two values closest to target date.

^c Week 28 is only applicable to eGFR change from baseline efficacy analysis

Table D 2: Analysis Visits for Post-Treatment Safety Analysis

Analysis Visit	Label	Target Study Day (Reference Day is Days After Last Dose)	Analysis Window
40	4-weeks – Off Treatment	28	$7 \leq \text{Study Day} \leq 35$
80	8-weeks – Off Treatment	56	$36 \leq \text{Study Day} \leq 63$
120	12-weeks– Off Treatment	84	$64 \leq \text{Study Day} \leq 91$
240	24-weeks– Off Treatment	168	$92 \leq \text{Study Day} \leq 175$

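### The 8-, 12- and 24-week off-treatment safety windows hold almost only early stoppers and the 4-week window mostly completers, so the off-treatment time course confounds patient mix with recovery

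*SAP*

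**What the plan says.** SAP 12.1 splits laboratory, vital-sign and ECG values into on-treatment and off-treatment, and states that "off-treatment values will be summarized according to the analysis study windows" in Appendix D. Table D 2 there, headed "Analysis Visits for Post-Treatment Safety Analysis", gives four windows after last dose: 7–35 days (target 28), 36–63 (target 56), 64–91 (target 84) and 92–175 (target 168). SAP 5.4 fixes the clock: "days since last dose = visit (or event) date - date of last dose".

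Protocol 7.1 ends the schedule with an "in-person follow up visit at Week 28, four weeks after the end of treatment". Table 3 of the protocol puts the end-of-treatment visit at Day 168±3 and the follow-up at Day 196±3. Protocol 8.4.1 asks patients who discontinue drug to stay on the visit schedule if possible. Patients who terminate early get end-of-treatment assessments and one follow-up four weeks later (Table 3, footnote v).

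SAP 5.2.3 applies a different clock to part of the same data. It classifies every assessment through Week 24 by time from randomization, whatever the drug status, and uses time from last dose for post-treatment assessments.

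**The concern.** Four columns labelled 4, 8, 12 and 24 weeks off treatment will be read as one group of patients followed after stopping. If completers cannot reach the last three, those columns describe patients who stopped early. Protocol 8.4.1 lists among the reasons adverse events, clinical worsening and mandatory transaminase thresholds. The 4-week column would describe mainly patients who took drug to Week 24.

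A pooled mean can then move between columns although no patient's value changes. A laboratory abnormality could appear to persist or rebound months after stopping because the later columns hold the patients who stopped for it. A difference between arms in those columns compares two groups selected after randomization. No rule in SAP 12.1, 12.3, 12.4 or 12.5 separates the two kinds of patient.

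**Working it through.** **Inputs.** End of treatment Day 168±3, follow-up Day 196±3, and laboratory and vital-sign visits on Days 7, 14, 28, 42, 56, 112, 168 and 196 (protocol Table 3). Scheduled post-baseline ECGs on Days 168 and 196 only (same table). Windows from SAP Table D 2, and 130 planned patients from SAP 2.2. The early-stop rate is not visible in the documents. I assume 10% to 50%, equal in both arms, with last-dose days uniform over Days 1–164.

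**1. The plan's own figure.** 196 − 168 = 28 days, which matches the 4-week target in Table D 2.

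**2. Completers.** With both visits inside their windows, time since last dose runs from 193 − 171 = 22 to 199 − 165 = 34 days. That is always within 7–35 and never at 36 or more. To reach 36 days, the follow-up would have to fall on Day 201 (last dose Day 165) to Day 207 (last dose Day 171), 2 to 8 days past the visit window.

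**3. Last dose needed to reach each later window at the final visit.** Subtract the lower window limit from the visit day:

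| Window | Day 196 visit | Day 199 visit |
|---|---|---|
| 8-week (36 days) | by Day 160 | by Day 163 |
| 12-week (64 days) | by Day 132 | by Day 135 |
| 24-week (92 days) | by Day 104 | by Day 107 |

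**4. Early stoppers who keep the schedule.** Number of the 164 possible last-dose days that place a scheduled value in each window, and how many of those also give a 4-week value:

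| Reading | 4-week | 8-week (also 4-week) | 12-week (also 4-week) | 24-week (also 4-week) |
|---|---|---|---|---|
| Labs and vital signs, SAP 12.1 | 110 | 104 (50, 48%) | 84 (57, 68%) | 104 (77, 74%) |
| ECG, SAP 12.1 | 32 | 56 (28, 50%) | 56 (0) | 104 (0) |
| Only Week 28 timed from last dose (SAP 5.2.3) | 4 | 28 (0) | 28 (0) | 84 (0) |

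For ECG, a 4-week value needs a last dose on Days 133–164, a 12-week value Days 77–132 and a 24-week value Days 1–104. Neither later range meets the first.

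**5. Size of the columns, labs and vital signs, 130 patients, both arms together.** With stop rate d and all stoppers retained, completers = 130(1 − d), 4-week column = completers + 130d × 110/164, and later columns = 130d × 104/164, 84/164 and 104/164. At d = 20%: 104 completers; 104 + 26 × 110/164 = 121 at 4 weeks; completer share 104/121.4 = 86%. The bracketed figures assume half the stoppers terminate and give only a 4-week value.

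| Stop rate | Completer share at 4 weeks | 8 / 12 / 24-week n |
|---|---|---|
| 10% | 93% (92%) | 8 / 7 / 8 (4 / 3 / 4) |
| 20% | 86% (83%) | 16 / 13 / 16 (8 / 7 / 8) |
| 30% | 78% (74%) | 25 / 20 / 25 (12 / 10 / 12) |
| 50% | 60% (54%) | 41 / 33 / 41 (21 / 17 / 21) |

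**6. What this does to a mean.** Suppose early stoppers differ from completers by an amount D and nobody changes after stopping. Relative to completers, the 4-week mean is (1 − completer share) × D and the later mean is D. The column mean moves by completer share × D, or 0.86 D at a 20% stop rate, with no within-patient change at all.

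**The case against.** Several points on the other side have force.

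- **Completers are not strictly excluded.** SAP 5.2.1 accepts unscheduled laboratory values, and protocol 11.6 has drug-related adverse events and abnormal laboratory results followed to resolution. A late visit or a repeat test could put a completer in a later window. This stands, and a reader should not infer that the later columns can contain no completer. Tests repeated to follow an abnormality would, however, bring in selected completers.
- **The trend is not only a change of patients.** A reader might infer that it says nothing about recovery. Under SAP 12.1, 48%, 68% and 74% of the stop days giving an 8-, 12- or 24-week laboratory or vital-sign value also give a 4-week value, and changes are taken from each patient's own baseline. For these parameters the columns mix both sources. The stronger reading comes close only for ECG at 12 and 24 weeks, or for every parameter if SAP 5.2.3 governs.
- **Safeguards exist.** SAP 5 requires n in every continuous summary. The laboratory and vital-sign summaries are descriptive, and no off-treatment test between arms is specified. The line plots in SAP 12.3.2 stop at study Week 28. SAP 12.3.3 adds shift tables from worst on-treatment to worst off-treatment for ALT, AST and total bilirubin. All true, but n does not say who the patients are, and the added shift tables cover three tests without a time course.
- **Stop reasons may be administrative.** SAP 7.2 foresees a study-wide drug termination date. Such patients would be less selected and would lower the completer share, but the SAP does not identify them separately either.

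**Conclusion.** The point holds as a limited one. On the protocol schedule, and apart from a few late or unscheduled tests, the 8-, 12- and 24-week windows can be filled only by early stoppers. That follows from visit dates and needs no assumption about stop rates. That the 4-week laboratory and vital-sign column is mostly completers rests on the assumed range: their share runs from 93% at 10% stopping to 60% at 50% with full retention, or 54% at 50% if half terminate. The expected numbers in the later columns rest on the same assumptions.

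The off-treatment course therefore confounds patient mix with recovery. It does so completely for scheduled ECGs between 4 weeks and 12 or 24 weeks, and partly for laboratory values and vital signs under SAP 12.1. If SAP 5.2.3 governs so that only the Week 28 visit is timed from last dose, the overlap is zero for every parameter. The SAP does not say which clock prevails. No efficacy or treatment-emergent adverse event analysis depends on these tables.

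**What to change.** In SAP 12.1 and Table D 2:

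1. Present off-treatment summaries separately for completers (4-week window only) and early stoppers, and identify any patients stopped by a study-wide administrative decision.
2. For early stoppers, show the 8-, 12- and 24-week values as change from the same patient's last on-treatment value, or as a listing. State that neither a trend across the pooled columns nor a difference between arms in the later ones is to be interpreted.
3. Reconcile SAP 5.2.3 with 12.1 and Table D 2, so that each value taken after last dose but before Week 24 has one stated clock for the off-treatment safety tables.

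Keep the existing ALT, AST and bilirubin shift tables. They cover part of the need for those tests, but nothing comparable exists for other laboratory values, vital signs or ECG. The cost is SAP wording and table shells, with no new data. The drawback is a few more sparse tables.

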12.2. Adverse events and serious adverse events

Each treatment emergent AE (TEAE) will be coded using the Medical Dictionary for Regulatory Activities (MedDRA version 19.0). An AE is defined as any untoward medical occurrence in a patient regardless of its causal relationship to study treatment. A TEAE must have an onset or worsen in severity on or after the first dose of study drug and not more than 30 days after the date of the last dose of study drug. AEs with an onset greater than 30 days after the last dose of study drug, and therefore not treatment-emergent AEs (TEAEs), are classified as off-treatment AEs (OTAEs). Analyses described for TEAEs are also performed for OTAEs and tabulated separately.

A SAE is defined as an adverse event that results in death, is life-threatening, requires inpatient hospitalization or prolongation of existing hospitalization, results in persistent or significant incapacity or substantial disruption of the ability to conduct normal life functions, is a congenital anomaly or birth defect in the offspring of a patient taking the study drug, or is an important medical event. Important medical events are defined as events that may jeopardize the patient or result in medical or surgical intervention to prevent one of the outcomes listed above. The term “life-threatening” refers to an event in which the patient was at immediate risk of death at the time of the event.

Adverse events resulting from concurrent illnesses, reactions to concurrent medications, or progression of disease states will be reported. Conditions existing prior to the start of the AE collection period are considered concurrent medical conditions and are not recorded as AEs. If the patient experiences a worsening or complication of a concurrent medical condition, the worsening or complication will be recorded as an AE.

Each AE will be recorded as a single diagnosis. Accompanying signs and symptoms will not be recorded as additional AEs. Signs and symptoms will only be recorded if the diagnosis is not determined. Changes in laboratory tests values or ECG parameters will be recorded if they are determined to be clinically significant; however, abnormal test values or ECG findings will not be reported as AEs if they are the result of pathology for which there is an overall diagnosis.

Elective procedures performed to manage or treat conditions existing prior to the patient’s enrollment in the study are recorded in the patient’s source documents but not in the AE records. If a planned procedure is performed early because the pre-existing condition worsens, the worsening should be documented as an AE.

The investigator must report all SAEs observed or reported by the patient to Reata or designee, regardless of their relationship to the study drug or their clinical significance. SAEs must be followed to resolution or until the investigator deems the event to be chronic or the patient to be stable.

Causality of AE is classified according to the following criteria:

- Unrelated: This relationship suggests that the study drug and the event are not associated.
- Unlikely: This relationship suggests that the association between the study drug and the event is unlikely.
- Possible: This relationship suggests that treatment with study drug might have caused or contributed to the AE. That is, the event follows a reasonable temporal sequence from the time of study drug administration or follows a known response pattern to the study drug, but could have been produced by other factors.
- Probable: This relationship suggests that a reasonable temporal sequence of the event with the study drug administration exists and, based upon the known pharmacological action of the drug, known or previously reported adverse reactions to the drug or class of drugs, or judgment based on the investigator's clinical experience, the association of the event with the study drug administration seems likely.
- Definite: This relationship suggests a definite causal relationship between the study drug administration and the AE, and other conditions (concurrent illness, progression/expression of disease state, or concurrent medication reaction) do not appear to explain the event.

Severity is assessed according to the following criteria

- Mild: Symptoms causing no or minimal interference with usual social and functional activities
- Moderate: Symptoms causing greater than minimal interference with usual social and functional activities
- Severe: Symptoms causing inability to perform usual social and functional activities

The MedDRA dictionary will be used to classify all AEs reported during the study by system organ class (SOC) and preferred term (PT). All summary tables will include counts of patients with treatment-emergent adverse events (TEAEs). TEAEs are defined as those AEs that have an onset time either at or after the start of study drug administration and no more than 30 days after the last dose of study drug is administered. Furthermore, TEAEs may be AEs ongoing at the time of study drug initiation that increase in severity or become closer in relationship to study drug administration during the treatment period. AEs with missing start dates, but with stop dates either overlapping into the treatment period or missing, will be considered TEAEs.

An overall summary of TEAEs will be presented with the number and percentage of patients having a TEAE, a serious TEAE, a TEAE leading to study discontinuation, a TEAE with an outcome of death, a TEAE related to study drug (definitely, probably, or possibly related), or a severe TEAE. The overall incidence of TEAEs will be summarized by SOC and by SOC and PT

using the number and percentage of patients reporting an event and the number of events reported. The incidence of serious TEAEs and TEAEs leading to study discontinuation will be summarized in a similar manner. TEAEs will also be summarized by maximum severity (mild, moderate, or severe) and assessed relationship to study drug with the percentage of patients in each category. A TEAE with missing severity or relationship will be considered severe or related, respectively. If more than one TEAE is recorded for a patient within any SOC or PT, the patient will only be counted once. Serious TEAEs, TEAEs leading to study discontinuation, and TEAEs with an outcome of death will be presented in separate listings.

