3.2. Safety population

The safety population includes all patients who received at least one dose of randomized study drug. Patients who received at least one dose of bardoxolone methyl will be classified in the

bardoxolone methyl group. Patients who received at least one dose of placebo and no bardoxolone methyl will be classified in the placebo group.

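### Off-treatment AE percentages have no at-risk denominator: almost all observation past day 30 comes from patients who stop drug early, so the crude rates move with early stopping as well as with risk

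*SAP*

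**What the plan says.** SAP 12.2 splits adverse events by time since the last dose. Treatment-emergent events (TEAEs) run to 30 days after it. "AEs with an onset greater than 30 days after the last dose of study drug" are OTAEs, and for these the SAP says: "Analyses described for TEAEs are also performed for OTAEs and tabulated separately".

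The TEAE analyses carried over are patient counts and percentages. "An overall summary of TEAEs will be presented with the number and percentage of patients having a TEAE", and incidence by system organ class and preferred term is given "using the number and percentage of patients reporting an event", together with the number of events. No person-time rate is specified.

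On the population, SAP 12.1 says: "The safety analyses will include only patients in the safety population". SAP 3.2 defines it: "The safety population includes all patients who received at least one dose of randomized study drug". No separate N is named for OTAEs.

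On follow-up, Protocol 7.1 plans a "follow up visit at Week 28, four weeks after the end of treatment". Table 3 of the protocol puts the end-of-treatment visit at Day 168 and the final visit at Day 196, each with a window of 3 days either side. SAP 2.2.3 places last contact no later than the Week 28 visit. Protocol 8.4.1 asks patients who stop drug to stay for all visits if possible. Patients who leave the study early have termination assessments and one further visit four weeks later (Table 3, footnote v).

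On AE recording, Protocol 11.2.1.1 runs it to the final visit in Table 3, whereas Protocol 11.6 ends it 28 days after the final dose.

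**The concern.** A percentage of patients with an event is readable as a risk when most patients in the denominator could have been seen to have the event. For OTAEs most could not. A nominal completer leaves the study before the OTAE period opens on day 31, while a patient who stops drug at Week 4 and stays can contribute more than four months.

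Two things follow. A low OTAE percentage may be taken as evidence that little happens off drug when few patients were watched. And the arm with more retained early stoppers will show more OTAEs at the same off-drug risk. Unequal stopping is foreseeable, although its size is not given: Protocol 5.1.3 reports transaminase increases in almost all treated patients, with about 4% to 11% above 3 times the upper limit of normal, and Protocol 8.4.1 lists transaminase findings that require stopping.

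The sponsor evidently means to interpret this period. The SAP revision history lists off-treatment safety analyses as an addition in version 2.0, and Table D 2 sets windows out to day 175 after the last dose.

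**Working it through.** The plan gives no OTAE rate, denominator size or early-stop rate to reproduce, so the check starts from the visit schedule.

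**1. Off-drug follow-up of a completer** (Protocol Table 3, taking the last dose on the day of the end-of-treatment visit).
- Nominal: 196 − 168 = 28 days, which matches the stated four weeks.
- Shortest: 193 − 171 = 22 days. Longest: 199 − 165 = 34 days.

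**2. OTAE observation time** = max(0, final visit day − last dose day − 30), with the final visit at Day 196.
- Last dose Day 28: 138 days. Day 112: 54 days. Day 165: 1 day. Day 168: 0 days.

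**3. Completers who pass day 30 through the windows.** Assume each visit is equally likely to fall on any of its 7 days, independently: 7 × 7 = 49 combinations.
- Follow-up exceeds 30 days when the final visit's offset is at least 3 days later than the end-of-treatment offset: 4 + 3 + 2 + 1 = 10 combinations, and 10/49 = 20%.
- These patients have 1 to 4 days past day 30, on average 2. Over all completers the mean is 20/49 = 0.41 day.

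**4. Who supplies the person-time.** Assume early stops are uniform over Days 1 to 165, with follow-up to Day 196. The mean time past day 30 is then (165 + 1)/2 = 83 days per early stopper. With a share q stopping early and all retained, their part of the OTAE person-days is 83q / [83q + 0.41(1 − q)]:
- q = 10%: 8.3/(8.3 + 0.37) = 96%
- q = 20%: 16.6/(16.6 + 0.33) = 98%
- q = 30%: 24.9/(24.9 + 0.29) = 99%

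**5. Dilution.** Let q be the share observed past day 30 and r the risk among them. The crude percentage is q × r, the percentage among those observed is r, and the factor between them is 1/q. With an assumed r = 20% and the planned 65 per arm (SAP Appendix B.2):

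| q (assumed) | Observed past day 30, of 65 | Crude % | % among observed | Factor |
|---|---|---|---|---|
| 10% | 6.5 | 2.0 | 20 | 10 |
| 20% | 13 | 4.0 | 20 | 5 |
| 30% | 19.5 | 6.0 | 20 | 3.3 |
| 50% | 32.5 | 10.0 | 20 | 2 |

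The factors are the same at 100 per arm.

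**6. Counting the completers from step 3 as at risk.** The share becomes q + (1 − q) × 10/49, that is 28.4%, 36.3% and 44.3% at q = 10%, 20% and 30%. The factors fall to 3.5, 2.8 and 2.3. This treats 1 to 4 days of observation like several months, which is why a patient count alone is not enough.

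**7. Arm comparison at equal risk.** If 20% of one arm and 10% of the other are observed past day 30 (assumed) and r = 20% in both, the crude figures are 0.20 × 20% = 4% and 0.10 × 20% = 2%. The ratio is 2 whatever r is, because it equals 20%/10%.

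**8. The two AE recording rules.** Under Protocol 11.2.1.1 steps 2 to 7 apply. Under Protocol 11.6 recording ends on day 28 after the final dose, before the OTAE period opens, so the tables would be nearly empty in both arms.

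**The case against.** Much of the case on the other side stands.

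- **The denominator is not stated.** A reader might infer that the SAP prescribes the full safety population as the OTAE denominator. SAP 12.1 restricts who enters the safety analyses, and no sentence names an OTAE N. The full population is the only denominator the text supports, but this is an omission rather than a declared choice.
- **The at-risk group is not simply the early stoppers.** Visit windows let some completers pass day 30 by a few days. Patients who leave the study with only the visit four weeks later may have no OTAE time at all.
- **The size is not established.** It is tempting to call the rates several-fold too low. The readable text gives no stop rate. If many patients stopped drug early, for example because the sponsor ended the study (Protocol 7.4), the factor could be 2 or less.
- **The effect depends on the recording rule.** A reader might think the dilution arises under either cut-off. Under Protocol 11.6 the tables would be nearly empty, which is a different problem.
- **The stakes are limited.** SAP 12.2 plans no tests on adverse events. It reports event counts beside percentages and lists serious and fatal events, and SAP 7.2 tabulates exposure, follow-up and discontinuation by arm. A crude percentage of treated patients is also a conventional summary.
- **An at-risk denominator has its own weakness.** It selects patients by something that happens after randomisation.

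What this does not remove: event counts without observation time depend on early stopping in the same way, and none of the specified tables shows how many patients were followed beyond day 30.

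**Conclusion.** The point holds as a gap in a descriptive safety analysis. Following the SAP as written gives OTAE percentages equal to the share observed past day 30 times the risk among those patients. They understate risk in the patients observed, and they differ between arms whenever retained early stopping differs, even at equal risk.

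The structure follows from the documents. The size does not: factors of 10, 5, 3.3 and 2 correspond to assumed shares at risk of 10%, 20%, 30% and 50%, and factors of about 3.5 to 2.3 to assumed early-stop shares of 10% to 30% when completers with 1 to 4 extra days are counted. The person-time shares also assume uniform stopping and full retention. All of this presupposes that events are recorded to the final visit, which the protocol leaves unsettled.

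A reader might also infer that the right denominator would give an unbiased comparison of off-drug harm. It would not, because the group is selected after randomisation and may be small. The primary efficacy analysis and the TEAE tables are unaffected.

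**What to change.** In SAP 12.2:

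1. Report by arm the number of safety-population patients with AE follow-up beyond day 30 after the last dose. Use it as the OTAE denominator, or print it beside the crude percentage.
2. Add OTAEs per 100 patient-years, counting time from day 31 after the last dose to last contact.
3. Label the arm comparison descriptive, and say that the at-risk group is selected after randomisation and may be small.
4. Leave the TEAE tables as they are.

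Separately, reconcile Protocol 11.2.1.1 with Protocol 11.6 on when AE recording ends, and state in the SAP which rule the data follow. The denominator change does not settle this.

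The SAP part costs a few sentences and one derived variable: last contact date minus last dose date minus 30. SAP 2.2.3 and 5.4 already define the components, so no new data are needed. The price is small denominators, roughly 6 to 20 of 65 per arm at assumed shares of 10% to 30%, which readers would now see.
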